### 3.4 TERTIARY/EXPLORATORY ENDPOINT(S) ANALYSIS

#### 3.4.1 Definition of endpoint(s)

Multiple Sclerosis Functional Composite (MSFC)-3 is a multidimensional, three-component performance scale to assess the degree of impairment in MS patients. Here, the MSFC-3 score is defined as the average of the T25-FW, 9-HPT, and SDMT Z-scores. If any one of the T25-FW, 9-HPT, and SDMT Z-scores is missing, then MSFC-3 score is set to missing.

No evidence of disease activity-3 (NEDA-3) is defined as absence of all of the following:

- 6-month CDP
- Active MRI lesions (both new or enlarged T2-hyperintense lesions and Gd-enhancing T1-hyperintense lesions)
- Adjudicated MS relapse

EQ-5D-5L is a standardized health-related quality of life questionnaire that provides a simple, generic measure of health for clinical and economic appraisal. It consists of 2 pages, the EQ-5D descriptive system and the EQ visual analogue scale (VAS). The EQ-5D descriptive system comprises 5 dimensions: mobility, self-care, usual activities, pain/discomfort and anxiety/depression. Each dimension has 5 levels: no problems, slight problems, moderate problems, severe problems, and extreme problems. EQ-5D-5L health status will be converted into a single index value by using the value sets based on UK population and according to the crosswalk algorithm developed by B. van Hout (10). The index score is anchored at 1 (full health) with 0 (negative values) corresponding to states being as bad or worse than dead. The EQ VAS records the respondent's self-rated health on a vertical VAS ranging from 0 (worst imaginable health state) at the bottom to 100 (best imaginable health state) at the top. Overall, higher scores indicate high health utility.

For the purposes of this study, MS relapse is defined as a monophasic, acute or subacute onset of, new neurological symptoms or worsening of previous neurological symptoms with an objective change on neurological examination. Symptoms must:

- 1. be attributable to MS,
- 2. last for  $\geq 24$  hours, with or without recovery,
- 3. be present at normal body temperature (ie, no infection, excessive exercise, or excessively high ambient temperature), and
- 4. be preceded by  $\geq$ 30 days of clinical stability (including no previous MS relapse).

Confirmation of MS relapse will be based on EDSS score (provided by the Examining Investigator), based on the following definition:

• A confirmed MS relapse is one accompanied by a clinically relevant change in the EDSS score performed by the Examining Investigator, ie, an increase of at least 0.5 points in the EDSS score, an increase of 1 point on 2 functional scores, or an increase of 2 points on 1 functional score, excluding changes involving bowel/bladder and cerebral functional score compared to the previously available rating (the last EDSS rating that did not occur during a relapse).

#### 3.4.2 Main analytical approach

Summary statistics including mean, SD, median, interquartile range (Q1, Q3), minimum, and maximum will be provided for the following continuous data endpoints at scheduled visits over the study period including the EOS. Only non-missing data will be included. For change from baseline, only participants with baseline and post-baseline data will be summarized.

- EDSS score and change from baseline
- Number of Gd-enhancing T1 lesions and change from baseline
- Number of new Gd-enhancing T1 lesions
- Number of new/enlarging T2 lesions per 6-month interval
- T2 lesion volume and change from baseline
- Cumulative number of new T1-hypointense lesions
- T1-hypointense lesion volume and change from baseline.
- Number of phase rim lesions and change from baseline
- Normalized brain volume at screening and percent change in brain volume at post baseline time points
- Number of slowly evolving lesions at EOS compared to screening
- Volume of slowly evolving lesions at EOS compared to screening
- SDMT number of correct substitutions Z-score and change from baseline
- SDMT number of completed items and change from baseline
- CVLT-II standardized scores for total number correct and change from baseline
- CVLT-II standardized scores for total number of intrusions and change from baseline

- CVLT-II standardized scores for total number of repetitions and change from baseline
- MSFC-3 score and change from baseline
- T25-FW raw score and Z-score for leg function/ambulation and change from baseline
- 9-HPT raw score and Z-score for arm/hand function and change from baseline
- MSQoL-54 score and change from baseline for the 2 derived composite scores, 12 subscale scores and 2 single item scores
- EQ-5D-5L health state utility value score and change from baseline
- EQ VAS score and change from baseline

Plots of mean ( $\pm$ SD) and/or mean change ( $\pm$ SD) and/or median over time will also be provided for better visualization.

#### Time-to-event endpoints

Time-to-event endpoints include:

- Time to onset of sustained 20% increase in the 9-HPT for at least 6 months,
- Time to onset of sustained 20% increase in the T25-FW for at least 6 months
- Time to onset of a 4-point decrease in the SDMT confirmed over at least 3 months
- Time to onset of a 4-point decrease in the SDMT confirmed over at least 6 months

Participants with no event will be censored at the date of the last assessment for the endpoint. No imputation will be performed for missing data. These endpoints will be analyzed using similar statistical methods as for the primary analysis of time to onset of 6-month CDP.

#### **Binary endpoints**

Binary endpoints include:

- Proportion of participants with CDI confirmed over at least 6 months
- Proportion of participants with CDI confirmed over at least 6 months and maintained until the EOS
- Proportion of participants with NEDA-3 at Months 18, 24, 30, 36, and EOS

A Cochran–Mantel–Haenszel (CMH) test stratifying by age at screening (>40,  $\leq$ 40 years) and region (US, non-US) will be used and the relative risk ratio on tolebrutinib compared to placebo with 95% CI will be estimated.

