 To evaluate pharmacodynamics (PD) of SAR442168 	 Change in plasma NfL levels at the EOS compared to baseline Change in lymphocyte phenotype subsets in whole blood a the EOS compared to baseline in a subset of participants Change in serum immunoglobulin level at baseline compared to the EOS
	Change in serum Chi3L1 levels at baseline compared to th EOS verse event of special interest; CDI, confirmed disability improvement; CD

Abbreviations: 9-HPT, 9-hole peg test; AE, adverse event; AESI, adverse event of special interest; CDI, confirmed disability improvement; CDP, confirmed disability progression; Chi3L1, chitinase-3-like protein 1; ECG, electrocardiogram; EDSS, Expanded Disability Status Scale; EOS, end of study; MRI, magnetic resonance imaging; MSQoL-54, Multiple Sclerosis Quality of Life-54 Questionnaire; NfL, neurofilament light chain; PD, pharmacodynamic; PK, pharmacokinetic; nrSPMS, non-relapsing secondary progressive multiple sclerosis; T25-FW, timed 25-foot walk.

Property of the Sanofi Group - strictly confidential

Overall design:

This is a Phase 3, randomized, double-blind, 2-arm, placebo-controlled, parallel group, multicenter, event-driven (6-month CDP) trial with a variable treatment duration ranging from approximately 24 to 48 months in participants with NRSPMS.

Disclosure Statement: This is a parallel treatment study with 2 arms that is blinded/masked for participants, the Investigator, any Investigator site staff, and the Sponsor.

Number of participants:

Approximately 1700 people will be screened to achieve up to 1290 participants randomly assigned to study intervention.

Enrolled participants will be randomly assigned at a ratio of 2:1 to 60 mg (established from dose-finding Study DRI15928) of oral, daily SAR442168 or daily matching placebo. Randomization will be stratified by age at screening (>40 versus \leq 40 years) and geographic region (US versus non-US).

Note: "Enrolled" means a participant's, or their legally acceptable representative's, agreement to participate in a clinical study following completion of the informed consent process. Potential participants who are screened for the purpose of determining eligibility for the study, but do not participate in the study, are not considered enrolled, unless otherwise specified by the protocol.

Intervention groups and duration:

Study intervention(s)

Investigational medicinal product(s)

- Formulation: SAR442168 film coated tablet
- Route(s) of administration: oral

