9.2 SAMPLE SIZE DETERMINATION

Approximately 1700 participants will be screened to achieve up to 1290 randomly assigned to study intervention (2:1 randomization ratio of SAR442168 to placebo). This study is planned as an event-driven trial based on 6-month CDP. The study will continue until approximately 288 events are projected to have occurred to provide 80% power to detect a 30% risk reduction in 6-month CDP with SAR442168 compared to placebo (2-sided α =0.05). The following assumptions were used for the calculations: 2-year placebo event rate of 23.6%; annual discontinuation rate of 10%; constant hazard rates using a log-rank test; estimated enrollment period of 24 months with last randomized participant followed for 24 months.

Actual recruitment and disability event rates may vary; therefore, it is possible to stop with a reduced sample size of around 1100 and still maintain study power by extending the duration of the trial, if needed, to reach approximately the same number of events. For example, it could be that the last randomized participant is followed for around 30 months instead of 24, if necessary. Additional recruitment of participants will not substantially reduce the trial duration. In any case, the power is based on the number of events, and the actual trial duration will be dependent on the observed placebo rate and treatment effect.

Note: "Enrolled" means a participant's, or their legally acceptable representative's, agreement to participate in a clinical study following completion of the informed consent process. Potential participants who are screened for the purpose of determining eligibility for the study, but do not participate in the study, are not considered enrolled, unless otherwise specified by the protocol.

Amended Clinical Trial Protocol 12 SAR442168-EFC16645 - tolebrutinib 20-Dec-2023 Version number: 1

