## **3 STATISTICAL ANALYSES**

#### 3.1 GENERAL CONSIDERATIONS

The baseline values of efficacy parameters are generally defined as the last available value prior to the first dose of study medication unless otherwise specified. In most cases the assessment should be prior to the randomization call, but it is possible that some assessments are performed between the actual randomization call and the first intake of investigational medicinal product (IMP). For the Expanded Disability Status Scale (EDSS) score, the baseline value will be taken as the average of the screening and randomization visit values. If one of the values is missing, the non-missing value will be used as baseline. The baseline value of safety parameters is defined as the last available value prior to the first dose of IMP. For the C-SSRS, the baseline value will be the worst assessment between the past 6 months evaluation at screening and the C-SSRS since last visit evaluation on Day 1. For participants randomized but not treated, the baseline value is defined as the last available value before randomization. Unless otherwise indicated, 2-sided p-values and 95% confidence intervals (CIs) will be provided for treatment comparisons.

To include all participants in analyses where baseline Gd-enhancing T1-hyperintense lesion presence or absence is used as a covariate, baseline status (present or absent) will be imputed for participants with a missing baseline count: if subsequent post-baseline counts for a participant are all 0, then impute baseline status as absent, otherwise, impute baseline status randomly with seed = 16645 based on the proportion of presence/absence at baseline in the overall population. Of note, the number of participants affected is minimal with no impact on results.

In general, continuous data will be summarized using the number of observations available, mean, standard deviation (SD), median, interquartile range (Q1, Q3), minimum, and maximum. Categorical and ordinal data will be summarized using the count and percentage of participants. Efficacy data will be analyzed in the ITT population, and safety data will be analyzed in the safety population, unless specified otherwise.

Unless otherwise specified, analyses will be performed by treatment group and overall for baseline and demographics characteristics.

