#### Other endpoints

Data for magnetization transfer ratio (MTR) recovery at EOS in new MTR lesions detected at Months 6 and 12 and normalized T1 intensity in SELs will be listed.

Actigraphy sub-study data will be collected and processed by an external vendor, Koneksa. Analysis and reporting of this sub-study will be performed separately from the CSR.

Missing data will not be imputed in the analysis of tertiary endpoints, nor will sensitivity or subgroup analyses be conducted.

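### NEDA-3 is compared as a raw proportion at fixed visits although follow-up varies by design, and the SAP gives no denominator or score for participants still event-free when follow-up ends before the visit

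*SAP*

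**What the plan says.** The binary endpoints in SAP 3.4.2 include "Proportion of participants with NEDA-3 at Months 18, 24, 30, 36, and EOS". They are compared by a CMH test stratified by age and region, and "the relative risk ratio on tolebrutinib compared to placebo with 95% CI will be estimated".

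The definition in SAP 3.4.1 begins "No evidence of disease activity-3 (NEDA-3) is defined as absence of all of the following" and lists 6-month CDP, active MRI lesions and adjudicated relapse. Protocol 8.1.7.2 gives the same components. Neither says what follow-up is needed before a participant can be called NEDA-3.

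On incomplete data, SAP 3.4.2 (Other endpoints) says: "Missing data will not be imputed in the analysis of tertiary endpoints, nor will sensitivity or subgroup analyses be conducted". SAP 3.1 adds "Efficacy data will be analyzed in the ITT population", that is, all randomized participants.

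The Protocol synopsis describes a "variable treatment duration ranging from approximately 24 to 48 months", ending at a common study end date. Protocol 9.2 assumes an "annual discontinuation rate of 10" percent, 24 months of enrollment and 24 months of follow-up for the last participant. It allows about 30 months instead if the sample is reduced to around 1100. SAP 1.1 gives a minimum of roughly 18 to 24 months.

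**The concern.** A participant who fails before the visit has a known NEDA-3 status, however early they leave. A participant who is event-free when follow-up stops does not. In a trial with a common end date this is not ordinary missing data, because a large share cannot reach Month 36 however well the study is run. EOS falls at a different follow-up length for each participant.

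The ITT statement does not settle the matter, since everyone in an ITT denominator still needs a status. At least four scoring rules are compatible with the text. If they give different Month 36 proportions and risk ratios, the reported result depends on a choice that could be made after unblinding, with no sensitivity analysis to show its influence.

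The MRI schedule adds to the gap. Scans are yearly after Month 24 and SAP Table 7 has no MRI window at Month 30, so the MRI component of a Month 30 status is undefined.

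**Working it through.** **1. The plan's own figures.** The documents give no figure for unscored NEDA-3, so the check starts with the design inputs. With 288 events, 2:1 allocation, hazard ratio 0.70 and two-sided 0.05, Schoenfeld gives z = √(288 × 1/3 × 2/3) × |ln 0.70| = 8 × 0.357 = 2.85. Power is Φ(2.85 − 1.96) ≈ 81%, against the stated 80%. With uniform accrual and 10% annual dropout, expected events are about 304 for 1290 participants with a 24-month minimum, and about 289 for 1100 with a 30-month minimum. The accrual and dropout inputs are therefore usable as stated.

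**2. Share of all participants not reaching a visit.** Share = 1 − (1 − late) × 0.9^t, where t is the visit in years and "late" is the share randomized too late to reach it. Visits use the plan's 28-day months: Months 18, 24, 30 and 36 are 1.380, 1.840, 2.300 and 2.760 years. Follow-up is taken as uniform over 2 to 4 years.

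| Visit | Late | Dropout | Not reached |
|---|---|---|---|
| Month 18 | 0 | 13.5% | 13.5% |
| Month 24 | 0 | 17.6% | 17.6% |
| Month 30 | 15.0% | 21.5% | 33.3% |
| Month 36 | 38.0% | 25.2% | 53.6% |

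For Month 36, late = (2.760 − 2)/2 = 0.38, and 1 − 0.62 × 0.748 = 0.536.

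The Month 36 figure depends on conventions:
- 24-month minimum: 54% as above, 63% with every month 28 days, 64% with every month a calendar month.
- 30-month minimum: 35% to 45%.
- 18-month minimum (SAP 1.1): 72% to 82%, with Month 24 then at 32% to 39%.

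**3. Share both event-free and unscored.** This needs NEDA-3 rates, which the documents do not give. Assume exponential failure, two-year placebo NEDA-3 of 40% to 50%, and failure hazard ratios of 0.6 to 0.7. The unscored share is 1 − (failures observed by t) − (event-free and observed at t). At Month 24 it is about 12% to 14%. At Month 36 it is 24% (placebo) and 33% (tolebrutinib) in the 40%/0.6 case on the 24-to-48-month plan. It is about 18% to 40% across the 24- and 30-month minimums, the month conventions and these rates.

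**4. Month 36 result under each scoring rule** (40% placebo, hazard ratio 0.6, equal dropout, 24-to-48-month follow-up). True values are 0.40^(2.760/2) = 28.2% and 0.40^(0.6 × 2.760/2) = 46.8%.

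| Rule | Placebo | Tolebrutinib | RR |
|---|---|---|---|
| Status known for all | 28% | 47% | 1.66 |
| Count failures, drop event-free leavers | 17% | 32% | 1.86 |
| Leavers scored as failures | 13% | 22% | 1.66 |
| Leavers scored as NEDA-3 | 37.5% | 54.5% | 1.45 |
| Only those reaching the visit | 28% | 47% | 1.66 |

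Scoring leavers as failures multiplies both arms by the same 0.464 (= 1 − 0.536), so the ratio survives although both proportions are more than halved. Using only those who reach the visit is unbiased here but discards failures already observed among the rest. The variance of its log ratio is about 1.6 times that of the Kaplan-Meier log ratio (1.56 by simulation, 1.61 from the asymptotic formula).

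**5. Other assumptions.** With placebo NEDA-3 of 50% at Month 24 and hazard ratio 0.70, the Month 36 RR is 1.37 with status known, 1.49 dropping event-free leavers, 1.37 with leavers as failures and 1.27 with leavers as NEDA-3. With no treatment effect and equal dropout, every rule gives about 1.00. At Month 24 in the 40%/0.6 case, dropping event-free leavers moves the RR only from 1.40 to 1.43.

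**The case against.** A reader might infer that the SAP keeps failures and drops event-free leavers. It does not say so. The ITT statement points towards a full denominator. The Table 7 convention that an empty window is missing, taken with no imputation, points towards those observed at the visit. Keeping failures while dropping event-free leavers is a third reading, and the risk ratio is preserved under the first (leavers as failures) and the second when censoring is equal in the arms. That stands.

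A reader might also attach the 18% and 54% to event-free participants. They are shares of all participants; the event-free and unscored group is smaller (step 3). On the 24-month plan nobody is randomized too late for Month 24.

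Nor is it right that everyone who stops treatment before Month 18 lacks a Month 18 scan. Later scans are annual, but the premature end-of-treatment visit includes an MRI that maps to the closest scheduled visit.

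Finally, NEDA-3 is exploratory, and its components have their own analyses with censoring or an exposure or scan offset. One sentence on the denominator would close the specification gap. That limits the importance of the point but does not remove it: each CMH denominator either distorts the Month 36 proportions or discards known failures.

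**Conclusion.** The point holds as a gap in specification combined with a method poorly matched to variable follow-up. The size at Month 36 is material: under the assumed 40% and 0.6, placebo NEDA-3 could be reported anywhere from 13% to 37.5% against a true 28%, and the RR from 1.45 to 1.86 against 1.66. At Month 24 the effect is small.

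The documents do not support a claim of false positive findings. With equal dropout no rule produces an effect under the null, and NEDA-3 lies outside the testing hierarchy in SAP 3.5, so type I error control is untouched. These magnitudes rest on assumed NEDA-3 rates, exponential failure times, and censoring that is independent and equal across arms.

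**What to change.** Analyse NEDA-3 as time to first failure: onset of 6-month CDP, adjudicated relapse or first active scan, whichever comes first, censored at the last complete assessment. Report Kaplan-Meier NEDA-3 proportions, with a difference or ratio and 95% CI, at visits with a scheduled MRI (Months 18, 24 and 36, not Month 30). Add a Cox hazard ratio with the primary-model covariates. SAP 3.4.2 already censors its other tertiary time-to-event endpoints at the last assessment, so the method is in place.

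If the CMH test is kept, restrict it to participants whose scheduled follow-up covers the visit, and state how event-free early leavers are scored.

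The cost is SAP wording and one extra derivation. The drawbacks are that non-informative censoring is assumed and that MRI failures are dated at the scan, which is only annual after treatment discontinuation.

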#### **Count endpoints**

Count endpoints include:

- Annualized adjudicated relapse rate
- Total number of new Gd-enhancing T1-hyperintense lesions

A negative binomial model will be used to analyze total count occurring during the observation period, adjusting for treatment group, age at screening (>40,  $\leq$ 40 years), region (US, non-US), baseline EDSS score and baseline Gd-enhancing T1 lesion (present, absent). Log transformed post-randomization observation duration or number of scans will be the offset variable. The estimated mean rates/numbers for each treatment group with the corresponding 95% CI, and the relative reduction on tolebrutinib compared to placebo with the 95% CI will be estimated.

#### **Continuous endpoints**

Continuous endpoints include:

- Change from baseline in MSFC-3 Z-score at Months 12, 18, 24, and EOS
- Change from baseline in total volume of T2-hyperintense lesions at Months 18, 24, and EOS
- Change from baseline in EQ-5D-5L descriptive system index score and VAS score by visit

An MMRM method will be used for these endpoints, including covariates of treatment group, age at screening (>40,  $\leq$ 40 years), region (US, non-US), visit, treatment-by-visit interaction, the baseline score, and baseline-by-visit interaction. Least squares means  $\pm$  SE for each treatment group, as well as LSM difference with the 95% CI will be estimated.

Since volume data are often non-normally distributed, analysis of T2 lesion volume will be performed on log-transformed volume data. MSFC-3 and EQ-5D-5L data are assumed a priori to be normally distributed. Given the large sample size, the impact of violation of normality should not be great. In order to assess the impact of deviation from the normality assumption, a sensitivity analysis using rank ANCOVA, with the same covariates as for the MMRM analysis except VISIT and related interaction terms, will be performed to test the significance of the treatment effect.

